3.0 Background*

Total hip arthroplasty (THA) is a widely successful and common orthopedic intervention used to replace damaged hip joints with artificial components; however, femoral component-related complications such as early subsidence, aseptic loosening, and periprosthetic femoral fractures (PPFs) continue to challenge long-term outcomes. Recent attention has focused on femoral stem design modifications—particularly the addition of a collar—to enhance primary stability and reduce the risk of early failure. The rationale for collar usage lies in its theoretical ability to provide mechanical support at the calcar, thereby preventing stem migration and improving load transfer in uncemented femoral stems.

The release of the ACTIS Hip Stem (DePuy Synthes, 2018) has contributed to a resurgence in the use of collared stems, prompting renewed clinical inquiry into their comparative performance. Despite encouraging early results, the current evidence remains incomplete. Notably, most data derive from retrospective series or registry-based analyses, which are inherently subject to selection bias and inconsistent reporting standards, particularly concerning intraoperative PPFs and stem revisions. Additionally, DePuy Synthes has recently released the exact same stem without a collar for similar use in primary THA.

MOD00024127

Page 3 of 18

Revised: November 12, 2025 IRB Approved

12/18/2025 - 11/3/2026

PROTOCOL TITLE: Comparison of clinical and radiographic results of collared and collarless femoral stems in total hip arthroplasty

Recent studies suggest that collared stems may indeed reduce the incidence of PPFs. Favroul et al. observed a significantly lower 90-day PPF rate in the collared stem group (0.4%) compared to the collarless group (1.6%) in a cohort of 1,623 THAs ($p = 0.048$). Aseptic loosening, a leading cause of THA failure, may also be mitigated by the use of a collared design. In a Swiss National Joint Registry study of over 30,000 THAs, collared Corail™ stems had a significantly lower revision rate for aseptic loosening (0.47%) than collarless stems (0.73%; $p = 0.022$).

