Perhaps most compelling is the growing body of evidence linking collared stems to reduced femoral stem subsidence—an early indicator of mechanical instability and a predictor of later aseptic loosening. A randomized controlled trial using radiostereometric analysis (RSA) found that collared stems exhibited significantly less subsidence than collarless stems at two weeks postoperatively (mean difference 2.23 mm; $p = 0.023$), although the difference diminished by one year. Additional studies using non-invasive EBRA (Ein-Bild-Röntgen-Analyse) confirm that collared stems consistently demonstrate lower average subsidence over 6 to 18 months.

Despite promising preliminary data, several gaps in the literature persist. For example, intraoperative PPFs are typically treated intraoperatively and may lead to a change in the femoral component type that is utilized. Often, this is not captured in retrospective reviews or during chart assessment even with prospectively collected data. Such arguments support the necessity of a controlled, prospective study directly comparing collared and collarless stems with standardized measurement of femoral stem subsidence and documentation of associated complications such as aseptic loosening and PPF. Furthermore, the clinical significance of early migration differences observed with various imaging modalities has not been fully elucidated, nor has their correlation with long-term outcomes been firmly established.

This proposed randomized controlled trial seeks to address these gaps by comparing the clinical and radiographic outcomes of collared versus collarless femoral stems in THA, using femoral stem subsidence as the primary endpoint and incidence rates of PPF, aseptic loosening, and PROMs as key secondary endpoints. By employing standardized radiographic measurements and robust follow-up, this study will offer high-quality evidence to inform implant selection and optimize surgical outcomes. It will also contribute to the development of clinically relevant thresholds for subsidence that can serve as early predictors of implant failure.

References:

<https://doi.org/10.1016/j.jor.2024.01.013>

MOD00024127

Page 4 of 18

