- Subsidence will be quantified using standardized radiographic measurement techniques. Typically, radiographs are obtained at 6 weeks, 6 months and annually thereafter. Calibration will be performed with the known femoral head size and subsidence measured by standard techniques on these serial radiographs.

Adverse Event Monitoring (Ongoing):

- Any PPFs or aseptic loosening will be identified through clinical assessment, imaging review, and/or surgical reports, and reported by trained investigators or study staff.
- Participants will be advised to report any fall or unusual hip symptoms. Any clinically indicated imaging or intervention will be reviewed for endpoint classification.

Risk Minimization:

- All surgeries will be conducted by experienced orthopaedic surgeons within the MedStar Health System (MedStar Georgetown University Hospital and MedStar Washington Hospital Center) to minimize procedural variability.

MOD00024127

Page 7 of 18

Revised: November 12, 2025 IRB Approved

12/18/2025 - 11/3/2026

PROTOCOL TITLE: Comparison of clinical and radiographic results of collared and collarless femoral stems in total hip arthroplasty

- Standard sterile technique and perioperative protocols will be followed.
- Follow-up visits coincide with routine care to minimize patient burden.
- Radiographic measurements will be conducted by independent reviewers to reduce measurement error and bias.
- There is no additional physical risk to participating in this study beyond standard of care.
- The primary risk is a potential breach of confidentiality. To minimize this risk, all data will be de-identified and stored on password-protected, HIPAA-compliant platforms. Participants will be assigned a unique study ID (SID), and any linkage to identifiable information (e.g., MRN) will be stored separately in a secured, password-protected file. No patient names or identifiers will be recorded on any data collection forms.
- Study participants will be made aware about the risk of randomization for the implant they will receive. By participating in the study, the surgeons will not be able to choose the implant.

Devices Used:

- Collared and collarless femoral stems, both commercially available and FDA cleared for primary THA use—the ACTIS Hip Stem that comes in both a collared and collarless variation, will be used.
- Both stem types are used in current clinical practice and do not represent investigational use.

Source Records:

- Source documentation will include:

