 - Electronic medical records (EMR)
 - Operative reports
 - Imaging records (X-rays)
 - Clinic visit notes
- Patient-reported outcome forms—collected in OBERD, the standard platform at MedStar for collecting PROMs

Data Collected:

- Demographics and clinical variables: age, sex, BMI, comorbidities, Dorr classification.
- Operative data: stem type, surgical approach, intraoperative complications.
- Primary endpoint: femoral stem subsidence at 6 weeks, 6 months, and 1 year, measured in millimeters from standardized serial radiographs.
- Secondary endpoints:
 - PPF incidence (confirmed radiographically or operatively).
 - Aseptic loosening (evidenced by radiolucent lines, implant migration, or revision surgery).
- Other outcomes: functional scores (PROMs), adverse events, and reoperation rates.

MOD00024127

Page 8 of 18

Revised: November 12, 2025 IRB Approved

12/18/2025 - 11/3/2026

PROTOCOL TITLE: Comparison of clinical and radiographic results of collared and collarless femoral stems in total hip arthroplasty

Data Collection Methods:

- Radiographic analysis performed by independent reviewers blinded to group allocation.
- Adverse events recorded by research staff at each visit and during any interim visits.

Long-Term Follow-Up — Patients will follow standard protocol for follow-up, offering the possibility of more longitudinal reporting potentially 5-10 years postop.

Humanitarian Use Device (HUD) — N/A

This study does not involve any HUDs. All devices used (collared and collarless femoral stems) are FDA-approved for standard use in primary THA and do not require an Investigational Device Exemption (IDE). The 510(k) number for the collared hip stem is K150862 and for the collarless version is K21058.

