17.0 Data Management* and Confidentiality

Femoral stem subsidence will be the primary outcome, measured in millimeters at 6 weeks, 6 months, and 1 year postoperatively. Differences in mean subsidence between the collared and collarless groups will be assessed using independent samples t-tests or nonparametric alternatives if assumptions of normality are not met. Incidence of PPF and aseptic loosening will be compared using chi-square tests or Fisher's exact tests. Logistic regression or Cox proportional hazards modeling will be used to adjust for covariates such as age, BMI, Dorr classification, and surgical approach if sample size allows. A sample size of 20 participants per group (40 total) provides 80% power to detect a difference of 0.4 mm in mean stem subsidence, assuming a standard deviation of 0.45 mm (based on prior RSA-based studies), with $\alpha = 0.05$. A proposed target enrollment of 100 participants is set to account for unforeseen dropouts.

All study team members will be trained in HIPAA compliance and Good Clinical Practice (GCP). Electronic data will be stored in a secure, password-protected, encrypted research database hosted on institutional servers. Subject identifiers (e.g., name, MRN) will be stored separately from study data and linked only via a unique coded identifier. Transmission of data between team members or collaborators will occur via encrypted institutional email or secure file-sharing platforms. No data will be shared externally without IRB and institutional approval.

Information Included:

- Demographic data, medical history, surgical details, implant type, radiographic images and measurements, and clinical outcomes (e.g., fracture, loosening, revision surgery).

Storage Location and Method:

- Data will be stored on secure, password-protected, encrypted institutional servers.
- Only authorized members of the research team listed on the IRB application will have access.
- The PI will oversee access and approve any data sharing requests.

18.0 Provisions to Monitor the Data to Ensure the Safety of Subjects – N/A

This proposed research study does not involve more than minimal risk to subjects, since it aligns with standard of care for THA procedures.

MOD00024127

Page 14 of 18 Revised: November 12, 2025 IRB Approved

12/18/2025 - 11/3/2026

PROTOCOL TITLE: Comparison of clinical and radiographic results of collared and collarless femoral stems in total hip arthroplasty

-

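### Aseptic loosening is defined with unqualified migration and revision of unstated cause, so it overlaps both the primary subsidence endpoint and the fracture endpoint

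*Protocol*

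**What the plan says.** The only working definition of loosening is in Protocol Section 6.0, under Data Collected: "Aseptic loosening (evidenced by radiolucent lines, implant migration, or revision surgery". It sets no amount of migration, does not ask that migration be progressive, and does not restrict the reason for revision.

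The same list gives the primary endpoint: "Primary endpoint: femoral stem subsidence at 6 weeks, 6 months, and 1 year, measured in millimeters from standardized serial radiographs". It gives fracture as a separate secondary endpoint, "PPF incidence (confirmed radiographically or operatively", and places reoperation rates among the other outcomes.

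On ascertainment, Section 6.0 says "Any PPFs or aseptic loosening will be identified through clinical assessment, imaging review, and/or surgical reports", and adds "Any clinically indicated imaging or intervention will be reviewed for endpoint classification". No criteria for that classification follow.

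Section 17.0 gives the analysis: "Incidence of PPF and aseptic loosening will be compared using chi-square tests", with Fisher's exact test as the alternative.

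Section 3.0 calls subsidence "an early indicator of mechanical instability and a predictor of later aseptic loosening" and hopes the trial will help establish subsidence thresholds that foretell failure. Its supporting registry figure is cause-specific: a "significantly lower revision rate for aseptic loosening (0.47%) than collarless stems", for which 0.73% is given.

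**The concern.** Two overlaps follow from the definition as written.

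- **With the primary endpoint.** Subsidence is migration of the stem, read on the same serial films. If migration is also evidence of loosening, one measurement feeds both the primary endpoint and a secondary endpoint reported as a separate complication. A modest difference in early subsidence could then be presented as a reduction in aseptic loosening. The protocol's wish to learn what degree of subsidence predicts failure would also become circular.
- **With the fracture endpoint.** The third aim (SA3) compares fractures and loosening as separate complications. With no cause attached to revision, a stem revised for periprosthetic fracture can count under both.

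The readers most affected are those who would take a loosening result as clinical confirmation of the radiographic one.

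**Working it through.** **1. The protocol's own figure.** Section 17.0 gives a difference of 0.4 mm, SD 0.45 mm, alpha 0.05 and 80% power. Taking the test as two-sided (sidedness is not stated):

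n per group = 2 × (1.960 + 0.842)² × 0.45² / 0.4² = 2 × 7.85 × 0.2025 / 0.16 ≈ 19.9, so 20.

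This reproduces the stated 20 per group; power at 20 is 80.3% by the normal formula and 78.2% by the exact t calculation. The protocol states no power for loosening.

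**2. What happens if migration beyond some cut-off is read as loosening.** Inputs from the protocol: SD 0.45 mm and difference 0.4 mm (Section 17.0), 50 per group (Section 12.0). Assumptions, because the protocol gives neither: arm means of 0.3 mm (collared) and 0.7 mm (collarless), and the cut-off c. Subsidence is taken as normal.

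Proportion labelled loose = 1 − Φ((c − mean) / 0.45).

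For c = 0.5 mm: collared (0.5 − 0.3)/0.45 = 0.444, giving 32.8%; collarless (0.5 − 0.7)/0.45 = −0.444, giving 67.2%. For c = 1.0 mm: z = 1.556 and 0.667, giving 6.0% and 25.2%. The other rows follow in the same way. Power is the exact probability that two-sided Fisher gives p ≤ 0.05 with 50 per group.

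| Assumed cut-off | Collared | Collarless | Fisher power |
|---|---|---|---|
| 0.5 mm | 32.8% | 67.2% | 92% |
| 1.0 mm | 6.0% | 25.2% | 69% |
| 1.5 mm | 0.4% | 3.8% | 1% |
| 2.0 mm | 0.01% | 0.2% | about 0% |

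**3. Sensitivity to the assumed means**, keeping the 0.4 mm difference (Fisher power):

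| Means (mm) | 0.5 mm | 1.0 mm | 1.5 mm | 2.0 mm |
|---|---|---|---|---|
| 0 v 0.4 | 86% | 19% | about 0% | about 0% |
| 0.3 v 0.7 | 92% | 69% | 1% | about 0% |
| 0.6 v 1.0 | 86% | 89% | 37% | about 0% |
| 1.0 v 1.4 | 37% | 89% | 86% | 19% |

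The range is about 0% to 92%. No true loosening enters the model, so every significant result here comes from the subsidence shift alone.

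**4. Scale of a cause-specific endpoint.** If the registry proportions in Section 3.0 applied, expected revisions for loosening would be 50 × 0.0047 + 50 × 0.0073 = 0.235 + 0.365 = 0.60 among 100 patients. The protocol does not give the registry's follow-up, and these are revisions, not radiographic cases, so this shows order of magnitude only.

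**5. The fracture overlap** needs no arithmetic. Fracture may be confirmed at operation, and revision is listed as evidence of loosening without a cause. A revision for fracture fits both descriptions, and nothing in Section 6.0 assigns it to only one.

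**The case against.** The best defence is that the endpoint is a diagnosis and the parenthesis lists signs that support it, without saying that each sign alone makes a case. Section 6.0 also provides for review before classification, with surgical reports available and radiographs read by blinded independent reviewers. A numerical migration limit is the kind of detail often left to an SAP, which is not at hand.

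Much of this is fair. The absence of a numerical limit is not itself the finding. A reader might infer that any migration whatever, or any revision whatever, counts as loosening. The text does not say so: it leaves both signs unqualified. A reader might also infer that revisions for infection are included, but the word aseptic excludes them.

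What remains is that the review has no stated criteria, so those applying it would have only the Section 6.0 definition to work from. Blinding protects against biased reading; it does not separate two endpoints built on the same measurement. An SAP would have to narrow the protocol's stated definition, not merely fill in a detail.

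**Conclusion.** The concern holds in a limited form. The stated definition lets the primary measurement re-enter as a secondary complication, against the Background's own distinction between predictor and outcome, and it allows a fracture revision to count twice within SA3. The primary analysis is unaffected.

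The 92% and 69% figures should not be read as the chance that this trial will report a spurious loosening difference. They rest on assumed means, an assumed normal shape, an SD that the protocol takes from RSA-based studies, and low cut-offs that the protocol does not adopt. At 1.5 and 2.0 mm, with the same means, power is 1% and about 0%. The supported conclusion is that the loosening result depends on an unstated cut-off. Nor do the 0.6 expected registry revisions estimate the number of truly loose stems in this trial.

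**What to change.** Revise the loosening definition in Section 6.0 as follows:

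- Count a revision only when its recorded indication is aseptic stem loosening.
- Do not let migration alone make a case unless it meets a prespecified progression criterion distinct from the primary endpoint. One form would be continuing migration between the 6-month and 1-year films beyond a limit fixed before outcomes are seen.
- Report all-cause revision only under the reoperation rate already collected.
- Have the review for endpoint classification apply these same criteria.

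This is a one-paragraph change using radiographs and records already planned. The cost is that fewer events will count as loosening. At the registry proportions there may be none, and a comparison on revision for loosening alone would have essentially no power at 50 per group. The endpoint would then be mainly descriptive.

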6.0 Procedures Involved*

This study is a prospective, randomized controlled trial comparing the clinical and radiographic outcomes of a collared versus collarless femoral stems of the same design in primary THA. A total of 100 participants undergoing elective, uncemented primary THA for degenerative hip disease will be enrolled.

Participants will be randomized in a 1:1 ratio to receive either a collared femoral stem or a collarless femoral stem. All patients indicated for a cementless primary total hip arthroplasty will be offered enrollment. Once consented, they will be randomized into the collared or collarless stem groups. Study participants will be informed about the risk of randomization due to removing the elements of choice from the clinician, as outlined in the informed consent form.

MOD00024127

Page 6 of 18

Revised: November 12, 2025 IRB Approved

12/18/2025 - 11/3/2026

PROTOCOL TITLE: Comparison of clinical and radiographic results of collared and collarless femoral stems in total hip arthroplasty

The primary endpoint is femoral stem subsidence, measured at postoperative 6week, 6-month, and 1-year clinical visits, which coincide with standard of care routine follow-up. Secondary endpoints include the incidence of PPF and aseptic stem loosening within the first postoperative year. Again, all research procedures are designed to align with standard perioperative and postoperative care for THA, minimizing burden for study participants. Additionally, the ACTIS Hip Stem (DePuy Synthes, Warsaw, IN) is routinely used by the participating surgeons for the last 3-4 years. The following outlines the specific protocol steps and time points:

Preoperative (Day -30 to 0):

- Obtain written informed consent either in person or via Interlace.
- Confirm eligibility criteria (inclusion/exclusion).
- Record baseline demographic data, diagnosis, and Dorr classification (from preop imaging).
- Randomization and group assignment.

Operative Day (Day 0):

- THA performed using the allocated femoral stem type (collared or collarless), via a standard surgical approach.
- Per standard practice, intraoperative documentation of any complications, including intraoperative PPFs, will be recorded by the surgical team.

Postoperative Follow-Up:

- Routine anterior-posterior (AP) pelvic and lateral hip X-rays will be obtained at 6 weeks, 6 months, and 1 year.

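### Readers of the primary endpoint are said to be blinded to allocation, but the allocated feature is a collar that the films would ordinarily show, and no masking is described

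*Protocol*

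**What the plan says.** The blinding statement is in protocol section 6.0, under Data Collection Methods: "Radiographic analysis performed by independent reviewers blinded to group allocation". Under Risk Minimization the same section relies on the same readers: "Radiographic measurements will be conducted by independent reviewers to reduce measurement error and bias".

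The arms are a collared and a collarless version of one stem. Section 3.0 says the manufacturer "has recently released the exact same stem without a collar for similar use in primary THA", and that the collar is meant to "provide mechanical support at the calcar", that is, at the proximal femur.

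The images and the measurement are described in section 6.0, Postoperative Follow-Up: "Routine anterior-posterior (AP) pelvic and lateral hip X-rays will be obtained at 6 weeks, 6 months, and 1 year", and "Calibration will be performed with the known femoral head size and subsidence measured by standard techniques on these serial radiographs".

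Section 4.0 makes subsidence the primary endpoint. Section 2.0 states the hypothesis that adding a collar reduces it. Section 17.0 sets the target difference at 0.4 mm.

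**The concern.** In this trial the allocation is a physical feature of the object being measured. A reader who opens an AP or lateral hip film to measure the stem would ordinarily see whether a collar is present, and so would know the arm. Keeping the allocation list and the patient's name from the reader does not change that.

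The protocol therefore claims protection against reader bias on its primary endpoint that it does not deliver as described. This matters because the hypothesis has a direction, the target difference is a fraction of a millimetre, and the measurement method is not specified closely enough to show how much reader judgement it allows. A trial report that repeated the blinding statement would overstate the strength of the evidence.

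The imaging part of aseptic loosening is exposed in the same way. The protocol defines it as "Aseptic loosening (evidenced by radiolucent lines, implant migration, or revision surgery"), and radiolucent lines and migration are read from films that show the stem. Loosening found through clinical assessment or revision surgery falls outside the reader-blinding statement.

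**Working it through.** **Step 1: can the statement hold?**

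| Element | What the protocol gives | Source |
|---|---|---|
| What defines the arm | Collar present or absent, otherwise the same stem | 3.0 |
| Where the collar acts | At the calcar | 3.0 |
| What the reader sees | AP pelvic and lateral hip films at 6 weeks, 6 months, 1 year | 6.0 |
| What the reader measures | Position of that stem over serial films, calibrated on the femoral head | 6.0 |
| What is hidden | Patient identity, through study IDs and separate storage of identifiers | 6.0, 17.0 |
| Means of hiding the collar | None described | – |

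The reader must view the proximal femur and implant to measure subsidence, and must view the nearby femoral head to calibrate. Nothing described hides the collar during that process. That it shows on the film is inferred from the device and the type of image; the protocol does not say so in words.

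**Step 2: the protocol's own sample size.** Inputs from section 17.0: difference 0.4 mm, SD 0.45 mm, power 80%, alpha 0.05 (taken as two-sided).

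n per arm = 2 × (1.960 + 0.842)² × (0.45/0.4)² = 19.9, so 20.

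This reproduces the stated 20 per group. The exact t-test gives power 0.78 at 20 per arm. The sample size is not in dispute; its inputs are used below.

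**Step 3: which kind of bias matters.** Subsidence is a change between a reference film and a later film. If a reader's error on a patient's films is *e*₀ at reference and *e*₁ later, the error in the change is *e*₁ − *e*₀. A constant offset (*e*₁ = *e*₀) cancels. An error that differs between films does not. If its mean differs between arms by *b*, then *b* appears as a treatment effect.

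**Step 4: illustration of the stakes.** Assume no true difference, so that only *b* separates the arms. The two-sided 5% two-sample t-test then rejects with the probability that a noncentral t variable with 2n − 2 degrees of freedom and noncentrality δ = b / (SD × √(2/n)) exceeds the critical value in absolute size.

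Example: n = 50, b = 0.2, SD = 0.45 gives δ = 0.2 / (0.45 × 0.2) = 2.22. The critical value is 1.984 and the rejection probability is 0.595.

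| n per arm | SD (mm) | b = 0.1 mm | b = 0.2 mm |
|---|---|---|---|
| 20 | 0.45 | 0.105 | 0.278 |
| 20 | 1.0 | 0.061 | 0.095 |
| 20 | 1.5 | 0.055 | 0.070 |
| 50 | 0.45 | 0.196 | 0.595 |
| 50 | 1.0 | 0.079 | 0.168 |
| 50 | 1.5 | 0.063 | 0.101 |

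From the protocol: SD 0.45 mm, and 20 and 50 per arm. Assumed: *b* (a quarter to a half of the 0.4 mm target), the SDs of 1.0 and 1.5 mm, and full analysis of 50 per arm. The larger SDs are included because 0.45 mm comes from RSA-based studies, whereas this trial measures plain films.

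At a fixed *b* and SD, moving from 20 to 50 per arm raises the false-positive rate. Enrolling more patients does not dilute this kind of bias.

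**The case against.** The strongest reply is that silence about the method is not impossibility. The protocol commits to blinded readers, nothing in it forbids masking, and reading procedures are often kept in an imaging manual that is not available here. On that view the fair criticism is only that the means of blinding is not stated. This limits the conclusion to the protocol as written. It does not remove it, because the statement is unqualified and the films described would undercut it unless a further step is taken.

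A second reply is that blinding to allocation may mean only that readers do not see the allocation list. If so, the wording misleads, because the film itself carries the allocation.

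Third, visibility of the collar is inferred. That is true, and the conclusion is worded accordingly.

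Fourth, the false-positive figures rest on an assumed bias and run from about 5% to 60%. The top value combines the largest assumed bias, the smallest SD and all 50 per arm. This stands: the figures show sensitivity and are not evidence that bias will occur. Independent readers and de-identified data also remain real, if partial, protections.

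Fifth, loosening is a secondary endpoint, and the text on identifying it claims no blinding. The point about loosening is therefore minor.

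**Conclusion.** The concern holds. As the protocol stands, readers can be kept from the allocation list, the patient's identity and the clinical outcome, but they cannot be blinded to stem type when they measure the primary endpoint. This is a stated safeguard that the intervention and imaging contradict, not a detail left for later.

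The conclusion rests on one inference: that an AP or lateral hip film ordinarily shows a collar. Its effect on the result cannot be sized from the document. Under the assumed bias, the false-positive rate could range from barely above nominal at the larger assumed SDs to several times nominal at the protocol's own SD. The matter should be corrected, but no sample size, test or visit has to change.

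**What to change.** **Preferred: make the blinding real for the subsidence reading.**

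- Have existing staff mask the medial neck and collar region on every film, with a mask that looks the same in both arms, leaving the femoral head visible for calibration.
- Measure from prespecified landmarks outside the masked area, for example the tip of the greater trochanter to the stem shoulder.
- Present films in random order, with patient ID and visit hidden.
- State that imaging assessment of loosening uses unmasked films and is not blinded to stem type.

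**Fallback if masking proves unworkable.** Reword the sentence under Data Collection Methods in section 6.0 to say that readers are not blinded to stem type but are kept unaware of patient identity, visit order and clinical outcome. Report this as a limitation.

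**Cost.** Masking covers 100 participants × 3 visits = 300 AP films, or 300 × 2 = 600 if lateral views are also measured. If a reference film before 6 weeks is used as well, the AP count is 100 × 4 = 400. Loosening needs a separate unmasked reading, and the choice of landmarks is restricted. The fallback costs one reworded sentence and a reported limitation. Neither option needs more patients or more visits.
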